Another novel aspect of this project will be the evaluation of baseline pain sensitivity, measured with field-based techniques, as a potential predictor of response to the interventions. Some patients with cLBP have a lower threshold for pain, due to an augmented central pain processing mechanism. As such, measures of pain sensitivity may prove useful in understanding an ongoing refractory pain-process; it is possible that patients who have a lower threshold for pain may respond differentially to behavioral interventions. In particular, these patients may experience greater improvement when CBT-P is offered as an additional program component (compared to PA alone), since these cognitive skills have been shown to influence pain processing. This pilot study will be an important step, ultimately leading to guidance regarding whether some older adults with cLBP should be offered a PA only vs. PA + CBT-P.

To our knowledge this will be the first study to examine the home-based PA only and PA + CBT-P programs among older adults with cLBP, as well as the first to evaluate central pain sensitivity as a predictor of response to these interventions. Therefore preliminary data are needed to support a larger project. Our specific aims are:

**Specific Aim 1:** Examine the feasibility of conducting 12-week home-based, telephone-supported programs of: 1.) PA only and 2.) Combined PA+CBT-P, among older veterans (65+ years) with cLBP. Quantitative measures of feasibility will include the proportions of patients who initiate and complete the programs and adherence to in-home PA recommendations and cognitive behavioral skills practice. We will also collect in-depth qualitative information to assess aspects of the interventions that may need to be modified prior to a larger study.

**Specific Aim 2:** Collect preliminary data to evaluate the efficacy of the PA only and PA + CBT-P programs among older veterans with cLBP. Main outcomes will be an objective test of general physical function (timed up-and-go (TUG)) and self-reported physical function (PROMIS Health Assessment Questionnaire (PROMIS-HAQ)). Secondary outcomes will include: Patient Specific Functional Scale (PSFS), Satisfaction with Physical Function Scale, LBP-specific disability (Roland-Morris Low Back Pain and Disability Questionnaire (R-MDQ)), and the Coping Strategies Questionnaire.

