### Central Pain Sensitivity May Predict Differential Response to PA for Low Back Pain

To date it has been challenging to understand why some individuals with cLBP respond favorably to evidence based interventions, such as PA, and others do not. One factor that may underlie this differential treatment response is central pain sensitivity. Findings from cLBP studies suggest that some patients have an augmented pain sensitivity, in which the pain experience results from or is exacerbated by abnormal pain processing rather than damaged or inflamed peripheral structures. As such, pain sensitivity may prove useful in understanding an ongoing refractory pain-process and particularly why some patients do not respond to a PA intervention alone. There is evidence that psychosocial characteristics such as pain catastrophizing and depression contribute to pain sensitization, and CBT-P can improve these psychological processes and outcomes. Therefore older adults with cLBP who have higher baseline pain sensitivity may respond better when PA is combined with CBT-P versus a PA program alone. However, this has not been investigated, and this pilot study will be an important step in this area of research.

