The baseline visit will include administration of consent, baseline questionnaires and functional assessments, and an examination by a physical therapist ([name]). During the physical therapist exam a Well Straight Leg Raise physical examination test will be used to determine the presence of ongoing sciatica, which may be exacerbated with physical activity. This test is conducted with the participant in supine position and the examiner supporting the non-involved leg. The examiner then raises the leg. A positive test is indicated if the participant reports concordant leg pain. This test is commonly used in clinical practice and is highly specific for sciatica (specificity=97%). Results of the physical therapist examination will be used to determine physical appropriateness for participation in the home-based PA program, based on the clinical expertise of the physical therapist and the criteria described below. If the physical therapist determines that the patient is not appropriate for participation in a home exercise program, the patient's primary care provider will be notified via response to the consult if the patient was referred by the provider, and that provider may refer the patient for more supervised physical therapy. All other non-qualified patients will have a progress note entered into CPRS stating that they may benefit from supervised physical therapy. During the baseline visit the participants will also receive a packet with several self-administered measures to fill out either at that time, or they can complete the questionnaires at home and then mail them back to the study team using a pre-addressed stamped envelope. We will monitor the return of these items and may need to do telephone follow-up calls to ensure that all measures are returned.

**Randomization:** Following the completion of all baseline assessments and the physical therapist examination, participants will be randomly assigned to one of the two intervention arms or to the wait list control group via an envelope selection procedure or by use of a randomization table programmed into the study tracking database. Randomization will be stratified by Central Sensitization Inventory (CSI) score (described below under Measures of Central Pain Sensitization), categorized by >40 vs. ≤40; this to ensure individuals with high vs. low pain sensitivity will be equally distributed across study groups.

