***Physical Activity Scale for the Elderly (PASE):*** The PASE is a brief self-report, 12-item scale that measures level occupational, household and leisure activity during a one-week period. This scale has good reliability ( $r=0.68$ ) and test-re-test reliability ( $r=0.75$ ). It has also been validated for telephone administration.

***Short Physical Performance Battery (SPPB):*** The SPPB is an objective assessment of physical function. This series of functional tests has been shown to predict hospitalization, disability, nursing home placement, and declines in health and function. This test battery is relevant to the study because it assesses aspects of daily function that require lower extremity strength and are often impacted by low back pain. Specifically, this battery examines participants' balance (3 tests), gait speed (8-foot walk), and time to rise from a chair and return to the seated position five times. We will follow previously established protocols for administering and scoring each of these tests. For each test, the possible range if scores is 0-4, for a total range of 0-20 for all five tests. We will also administer the 2-minute step test. These assessments will be conducted at baseline and 12-week follow-up.

**Measures of Central Pain Sensitization:** There are a several methods for measuring central pain sensitivity. For this study we have chosen field-based tests and a self-report measure because of their potential utility for use in clinical practice:

***Pressure-Pain Threshold (PPT):*** PPT is a safe, easily administered, low cost, and validated biological marker of pain sensitivity that has been commonly used in musculoskeletal conditions. This test involves using a digital device to measure the amount of pressure experienced by a participant. Consistent with established

protocols, PPT measurements will be collected from both the left and right upper trapezius muscle and lumbar spine erector spinae musculature at the level of L5 in a systematic fashion, with the first being a practice trial. Beginning with the left side, pressure will be applied to the muscle at approximately 1Kg per second until the participants indicate self-reported pain. Trials will continue until two consecutive readings were within +/-0.4 Kg's for a maximum of four trials. The same procedure will be repeated for the right side.

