**Analyses**: We will compare outcomes across study groups with analysis of covariance (ANCOVA) models (or non-parametric alternatives such as the Kruskal-Wallis test, when indicated), controlling for baseline values. Since this is a pilot study with small sample size, even clinically relevant differences may not be reflected as statistically significant differences (e.g. p<0.05). Therefore we will focus on effect sizes for the two intervention groups and evaluation of whether between-group difference reflects a threshold of clinical relevance. These data, along with means and standard deviations of baseline scores, correlations between baseline and follow-up scores, and attrition rate will also be used to calculate the appropriate sample size for a larger clinical trial. To address Aim 3, we will first plot baseline PPT and CSI values vs. changes in outcomes for each intervention group; we will also calculate correlations for these same associations. This will allow us to evaluate whether associations between baseline pain sensitivity measures and changes in outcomes may differ between the two intervention groups. Based on our previous experience with analyzing PPT data, we will also dichotomize these baseline scores at a <4kg vs. >=4kg to represent low and high pain sensitivity. We will then add an interaction term to our ANCOVA models (study group \* dichotomous PPT variable) to evaluate whether intervention effects vary by this indicator. If a significant interaction term is found, we will stratify the sample by this variable and explore the nature of the interaction. A similar analysis will be conducted with the established cutpoint on CSI scale or 40 out of 100.

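### The pressure-pain threshold cut is labelled backwards: read in order, <4 kg is called low sensitivity, but the protocol's own definitions make it high

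*Combined protocol and SAP*

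**What the plan says.** The Analyses paragraph (Research Design and Methods) sets the rule for the PPT moderator: "we will also dichotomize these baseline scores at a <4kg vs. >=4kg to represent low and high pain sensitivity". The resulting binary variable enters the ANCOVA as an interaction with study group. If the interaction is significant, the sample is split on that variable to see what form the interaction takes. A similar analysis is planned for CSI with a cut at 40.

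Other parts of the protocol fix what a low or high reading means:

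- **Measurement** (Measures of Central Pain Sensitization, PPT): "pressure will be applied to the muscle at approximately 1Kg per second until the participants indicate self-reported pain".
- **Mechanism** (Specific Aims): "Some patients with cLBP have a lower threshold for pain, due to an augmented central pain processing mechanism".
- **Hypothesis stated by threshold** (Specific Aims, of the lower-threshold patients): "these patients may experience greater improvement when CBT-P is offered as an additional program component".
- **Hypothesis stated by sensitivity** (Background and Significance, subsection on central pain sensitivity): "older adults with cLBP who have higher baseline pain sensitivity may respond better when PA is combined with CBT-P versus a PA program alone".
- **Companion measure** (Randomization): CSI is split at >40 vs. ≤40, with the purpose given as "this to ensure individuals with high vs. low pain sensitivity will be equally distributed across study groups".

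**The concern.** The cut lists <4 kg first and ≥4 kg second, and the labels list low first and high second. Paired in order, someone who reports pain at, say, 3 kg is classed as having low pain sensitivity, and someone who tolerates 5 kg as having high. That is the reverse of what a pain threshold measures.

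Aim 3 has a directional hypothesis: more sensitive patients should gain more from PA + CBT-P than from PA alone. If the labels are followed as written, a PPT result that supports this would be described as going against it. PPT would also appear to disagree with CSI when the two agree. The Specific Aims present the pilot as a step towards guidance on which patients should be offered PA alone or PA + CBT-P, so the direction of the moderator result is what a larger trial would carry forward.

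**Working it through.** The plan gives no figure to reproduce here. The check is whether the label agrees with the protocol's own definitions, and then what a swap changes.

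**Step 1: direction of the scale.** Pressure rises at about 1 kg per second until pain is reported, and the reading is the pressure at that point. A smaller kg value means pain at less pressure, which is greater sensitivity.

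**Step 2: direction of the hypothesis.** The Specific Aims expect lower-threshold patients to gain more when CBT-P is added. The Background expects the same of patients with higher sensitivity. These are one hypothesis in two wordings, so low threshold and high sensitivity describe the same group.

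**Step 3: side by side.**

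| Group | Label from Analyses, read in order | Label implied by Steps 1 and 2 |
|---|---|---|
| PPT <4 kg | low sensitivity | high sensitivity |
| PPT ≥4 kg | high sensitivity | low sensitivity |
| CSI >40 | not labelled there | high (Randomization paragraph) |
| CSI ≤40 | not labelled there | low (Randomization paragraph) |

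Nowhere does the protocol say that a higher PPT means greater sensitivity.

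**Step 4: what the swap changes.** Let L = 1 if PPT <4 kg and H = 1 − L. Let A indicate PA + CBT-P against PA. (The wait-list terms behave in the same way.) With L in the model:

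y = β0 + β1·baseline + γ·A + δ·L + θ·A·L

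Substituting L = 1 − H:

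y = (β0 + δ) + β1·baseline + (γ + θ)·A − δ·H − θ·A·H

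The fitted values are identical, so the interaction F and p are identical. The A contrast is γ + θ in the <4 kg group and γ in the ≥4 kg group under either coding. The interaction coefficient changes from θ to −θ, and the two contrasts exchange labels.

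**Step 5: illustration on assumed data.** None of the effect or variance inputs come from the protocol. The inputs are 60 people, 20 per arm; PPT with mean 4 and SD 1.2 kg; higher outcome better; outcome = 0.6 × baseline + 0.3 for either active arm + 0.8 more for PA + CBT-P when PPT <4 kg; residual SD 0.8.

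| Quantity | High = ≥4 kg (as written) | High = <4 kg (protocol's direction) |
|---|---|---|
| Interaction F, p | 2.593, 0.0843 | 2.593, 0.0843 |
| PA + CBT-P vs. PA interaction coefficient (SE) | −0.559 (0.545) | +0.559 (0.545) |
| PA + CBT-P minus PA in <4 kg group | +0.314, called low | +0.314, called high |
| PA + CBT-P minus PA in ≥4 kg group | −0.244, called high | −0.244, called low |

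The difference between the contrasts is 0.314 − (−0.244) = 0.558, which matches the coefficient up to rounding. A second assumed data set (PPT SD 1.5 kg, lower outcome better) behaves in the same way. F = 0.4622 and p = 0.6324 under both codings, and the coefficient is +1.23 as written and −1.23 corrected. The corrected signs differ between the two sets because the outcomes are scored in opposite directions.

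**The case against.** The strongest reply is that the sentence does not say *respectively*. Low and high may simply name the two categories without mapping them in order, and the rest of the protocol leaves only one coherent direction. It is also fair to say that no test, eligibility rule or randomisation stratum uses the label, because randomisation is stratified by CSI. The strata are defined in kg, and the raw plots and correlations come first and could expose a swap. The simulated figures only illustrate an algebraic identity. Neither simulated interaction reaches the p<0.05 that the plan cites as its example of significance, so at that level neither data set would have led to stratification. All of this concerns one exploratory step in a 60-person pilot.

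Most of that stands as a limit on size. It does not rescue the wording. The Randomization paragraph uses the same parallel construction for CSI, also without *respectively*, and there the in-order reading is the correct one. The PPT sentence is the only place where labels are attached to the PPT groups, and nothing later corrects it. Even if the intent was right, an analyst could reasonably code this rule backwards. The simulations show what a swap does, not how large a moderator effect to expect.

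**Conclusion.** The concern holds. As written, the PPT rule reverses the direction set by the protocol's measurement procedure and by its hypothesis. This conclusion rests on reading the sentence in order and on the protocol's own statements. The source cited for the 4 kg cut was not consulted and is not needed for the point.

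The effect is on interpretation. The sign of the dichotomised-PPT interaction coefficient and the names of any PPT strata would be reversed if the written labels are followed. Feasibility (Aim 1), the main efficacy comparisons (Aim 2) and the rest of Aim 3 are untouched. The sentence should be corrected before analysis, but the error does not threaten the trial.

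**What to change.** Replace the labelling in the Analyses paragraph with an explicit rule: PPT <4 kg = high pain sensitivity; PPT ≥4 kg = low pain sensitivity. Stating the two labels is the essential change.

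Two small additions guard against a repeat. Code the indicator as 1 for <4 kg, so that it runs the same way as CSI >40, and print the kg range beside the label wherever PPT strata are reported.

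The cost is one sentence in the analysis section. It needs no new data and no change to the cut-point, the model or the randomisation.

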## RESEARCH DESIGN AND METHODS

**Study Design:** This project will be a randomized controlled pilot trial of 12-week programs of PA only and PA + CBT-P, both supported by telephone, among 60 older adults with cLBP at the Durham VA Medical Center (VAMC). Participants will be randomly assigned with equal allocation to the two intervention groups or a wait-list control (WL) group. Participants will complete assessments at baseline, then approximately 12-weeks later. Participants in the WL group may choose to participate in the PA only or PA + CBT-P program following 12-week assessments. The 12-week follow-up was chosen because this is a reasonable time frame for older adults to experience neuromuscular adaptations and changes in general physical function. We chose a home-based exercise program because of its feasibility for widespread dissemination in the VA and because prior work has shown that home-based PA programs are safe and effective for improving physical function among older adults. We have chosen telephone-based approach because we expect this method of communication will be well received by older veterans, based on our prior and ongoing work in telephone-based PA support for osteoarthritis. We have chosen to include a control group in this pilot trial to account for any general improvement or changes in primary care intervention that may be observed in the course of cLBP. Participants will be paid \$30 for each assessment visit for time and travel.

**Participants and Recruitment:** The target sample for this study will include older veterans (65+ years) with cLBP at the Durham VAMC. We may over-sample women to ensure this important demographic group of Veterans is adequately represented in the study. In particular, we may prioritize contacting women Veterans who meet study entry criteria so that they comprise at least 30% of the study sample. We will have three recruitment mechanisms:

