**Inclusion / Exclusion Criteria:** Based on previous studies, we will **include participants who:**

- 1) Self-report having had lower back pain on most days for greater than three months.
- 3) Can complete a 10 second semi-tandem stand and walk 8' in 6.0 seconds.
- 4) Report they are not satisfied with their current state of functional ability, based on reporting "dissatisfied" with at least one aspect of physical function on the Satisfaction with Physical Function Scale.
- 5) Can safely participate in the intervention based upon the physical therapist baseline examination and clinical expertise.

Veterans will be **excluded if they have:**

- 1) acute unilateral or bilateral sciatica (based on Physical Therapist exam at baseline); isolated coccyx pain (based on self-report at screener);
- 2) dementia or other significant cognitive impairment;
- 3) movement or motor neuron disorders (e.g., Parkinson's Disease, Multiple Sclerosis, Amyotrophic Lateral Sclerosis);
- 4) rheumatoid arthritis, fibromyalgia, or other systemic rheumatic disease;

- 5) hospitalization for a stroke, myocardial infarction, heart failure, or coronary artery revascularization in the past 3 months;
- 6) significant hearing impairment (must be able to talk on the telephone);
- 7) psychosis or current, uncontrolled substance abuse disorder;
- 8) legally blind;
- 9) any other health conditions determined by the study team to be contraindications to performing mild to moderate home exercises.

Based on our prior and ongoing studies at the Durham VAMC that have similar recruitment and procedural methods, we are confident we can enroll n=60 older veterans with cLBP within the proposed recruitment period for this study. Study participants excluded after consent due to the presence of sciatica or other functional limitations or health problems as determined by the physical therapist at baseline will not be randomized and thus not included in our total enrollment goal, i.e. we plan to consent enough participants such that a total of n=60 are eligible to participate, having met the eligibility criteria assessed following consent.

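### The Aim 3 interaction models use PPT and CSI only as binary variables; a continuous group-by-marker term with an interval should be the main estimate, with the cut-points secondary

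*Combined protocol and SAP*

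**What the plan says.** The Analyses paragraph of Research Design and Methods takes Aim 3 in two stages.

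- **Descriptive, full scale.** "we will first plot baseline PPT and CSI values vs. changes in outcomes for each intervention group". Correlations for the same pairs follow. The stated purpose is to see whether the associations differ between the two intervention groups. No test, slope difference or interval is named, and the wait-list arm is left out.
- **Model-based, binary.** For PPT, "we will also dichotomize these baseline scores at a <4kg vs. >=4kg". Then "We will then add an interaction term to our ANCOVA models", the term being study group by the two-level PPT variable. For CSI, "A similar analysis will be conducted with the established cutpoint on CSI scale or 40 out of 100". No interaction with a continuous marker is planned.

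The trial is to run "among 60 older adults with cLBP at the Durham VA Medical Center (VAMC"), and "Participants will be randomly assigned with equal allocation to the two intervention groups or a wait-list control (WL) group". On the design side, "Randomization will be stratified by Central Sensitization Inventory (CSI) score", at the same cut of 40. PPT is not a stratification factor.

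The documents give no expected distribution of either marker and no expected share on either side of either cut.

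**The concern.** PPT is a reading in kilograms and CSI Part A runs from 0 to 100. Cutting them treats readings of 3.9 and 4.1 kg as opposites, and readings of 4.1 and 9 kg as the same. When a marker's effect changes gradually along its scale, the cut discards information that the trial has already paid to collect. An interaction estimated from 20 people per arm can ill afford that.

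If the cut also falls far from the middle of the sample, the interaction rests on very few people per arm and may not be estimable.

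At stake is the usefulness of Aim 3 for planning. The pilot is meant to inform later guidance on who should be offered PA alone and who PA + CBT-P. The quantity that serves this is how much the difference between those two arms changes with pain sensitivity, and how precisely that is known. Within-arm correlations do not supply it. They are not described as adjusted for baseline, and they can differ between arms simply because the marker's spread or the outcome noise differs.

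**Working it through.** The plan states no power, precision or information figure for Aim 3, so there is none to reproduce. The arm size follows from the total and the equal allocation: 60 / 3 = 20.

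**Assumptions, not in the documents.** The marker is roughly normal; its effect on outcome is linear; a share p of participants falls on the smaller side of the cut, with p = 0.5, 0.2 or 0.1.

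**Step 1. Information kept by a split.** The fraction kept is φ(z_p)² / [p(1 − p)], where φ is the standard normal density and z_p the cut-point.

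- p = 0.5: 0.3989² / 0.25 = 0.637, a loss of 36%
- p = 0.2: 0.2800² / 0.16 = 0.490, a loss of 51%
- p = 0.1: 0.1755² / 0.09 = 0.342, a loss of 66%

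Of the 40 people in the two active arms, the effective number is 40 × 0.637 = 25.5, 40 × 0.490 = 19.6 or 40 × 0.342 = 13.7. Under these assumptions about 36% is the smallest possible loss.

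**Step 2. Size of the smaller PPT cell.** PPT is not stratified, so the count on the smaller side in an arm is Binomial(20, p). The chance of one person or none in an arm is (1 − p)^20 + 20p(1 − p)^19.

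- p = 0.2: 0.0115 + 0.0576 = 0.0692
- p = 0.1: 0.1216 + 0.2702 = 0.3917

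| Split | Expected smaller cell per arm | One or none in at least one of three arms | Same, two active arms | Empty cell in at least one of three arms |
|---|---|---|---|---|
| 80/20 | 4 | 1 − 0.9308³ = 19% | 1 − 0.9308² = 13% | 3% |
| 90/10 | 2 | 1 − 0.6083³ = 77% | 1 − 0.6083² = 63% | 32% |

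The three-arm column applies to the full ANCOVA, the two-arm column to the PA versus PA + CBT-P contrast. At 70/30 the expected smaller cell is 6, and the chance of an empty cell in any of three arms is about 0.2%.

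**Step 3. CSI.** Randomisation is stratified at 40, so the binomial figures do not carry over: the arms should be close to balanced. Stratification cannot raise a low prevalence, however. If 10% scored above 40, that would be 6 of 60, or about 2 per arm.

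**Step 4. Effect on detection, for illustration.** The simulation used two arms of 20 and an ANCOVA with baseline, group, marker and group by marker, at two-sided 0.05. The assumed slope difference was 0.8 residual SD per marker SD.

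- **Linear truth.** Detection is about 62–63% with the continuous term. With the split it is about 46% (50/50), 32% (80/20) and a little under 20% (90/10). At 90/10 the binary interaction cannot be estimated in about 23% of data sets.
- **Step at the cut.** The order reverses: about 66% with the split against 44% continuous at 50/50, and about 60% against 32% at 80/20.

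**The case against.** The strongest reply has four parts.

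**Continuous use comes first in the plan.** The plots and correlations are there to compare associations between the two intervention groups. This stands to the extent that the loss sits in the interaction models and not in Aim 3 as a whole. A reader might infer that the trial throws away a third to two thirds of its marker information, but the documents do not support that. What the descriptive stage lacks is a baseline-adjusted slope difference with an interval.

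**The cuts have a rationale.** The plan cites a source for each, and calls 40 clinically relevant. The eventual decision, PA alone or PA + CBT-P, is also threshold-like, and under a true step the binary model does better. This stands, and is why the cut-point models should be kept. It does not make them the better main analysis, since nothing in the documents shows that response to these programmes changes abruptly at 4 kg or 40.

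**The pilot is not powered for interactions.** With a smaller assumed slope difference of 0.3, detection is about 15% continuous against 11% (50/50) or 8% (80/20), so neither version is a usable significance test. This also stands. But the Analyses section says the focus will be on effect sizes because significance is unlikely, and that favours an estimate with an interval.

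**Near-empty cells are not established.** A reader might infer that sparse cells are to be expected for both markers. The documents give no distribution, the risk is small near the middle of the scale, and CSI is balanced by stratification. The exclusion of "rheumatoid arthritis, fibromyalgia, or other systemic rheumatic disease" could thin the high end of CSI, but the documents give no figure from which to judge that.

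**Conclusion.** The point holds as a matter of precision and reporting. The Aim 3 interaction models use both markers only in binary form, and no continuous between-arm estimate with an interval is planned.

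The size is conditional. The loss of 36% to 66% requires an approximately normal marker and a linear effect, and its upper end requires a 90/10 split that the documents neither state nor exclude. Between 50/50 and 70/30 the loss is 36% to 42%. Under a step at the cut there is no loss, and the split is the more sensitive form.

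Sparse cells are a secondary concern that matters at about 80/20 or worse, mainly for PPT. Dropout, for which no rate is given, would shrink every cell further.

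The change should be made because it is cheap and yields the quantity Aim 3 needs. The documents do not show that the planned models will fail.

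**What to change.** In the Analyses section, make study group by continuous baseline PPT, and study group by continuous CSI Part A score, the main Aim 3 interaction terms in the ANCOVA. For each, report the difference in slope between PA and PA + CBT-P with a 95% interval. Keep the 4 kg and 40 cut-point models as secondary analyses, and report the number of participants in each arm-by-category cell beside them. Keep CSI above 40 versus 40 or below as the randomisation stratum.

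The cost is a few words of text, with no new data or visits. The small downside is that a linear term assumes a straight-line relation and is less sensitive to a true threshold. The scatter plots already planned and the retained cut-point models would help to show one.
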